#### 7.6.2.2 Post-transplant Safety Laboratory Parameters

Post-transplant safety laboratory parameters to be summarized include the following.

- AST, ALT, INR, PTT, fibrin degradation products, and C-reactive protein.

Samples for post-transplant safety laboratory parameters are taken at Days 1 through 7 post-transplant and on Day 75 ± 14 days for AST and ALT. Each parameter will be summarized descriptively at each applicable time point by treatment group and in total.

Change from baseline (screening) at each applicable follow-up time point will be summarized for AST and ALT by treatment group and in total. Change from baseline (screening) will be analyzed within a single repeated measurements model (for each of AST and ALT) using PROC MIXED within SAS®. The model will include fixed effect terms for site, time (Days 1 through 7 and 75), and treatment; the treatment by time interaction; the treatment by study site interaction if significant at the 0.10  $\alpha$ -level; baseline value as a covariate; and a random effect for patient. A compound symmetry covariance structure will be used to account for the multiple observations from the same patient.

The adjusted least squares means and associated 95% confidence intervals will be estimated for each combination of day and treatment, and the adjusted least squares mean difference (reparixin minus placebo) and associated 95% confidence interval at each day will also be estimated. The treatment effect within each day will be tested using a two-sided test at the 5% level. The tests of the fixed effects in the model will also be presented.

Observed values for all parameters will also be presented as box plots for each treatment group at each time point.

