### 6.3.2. Criteria for discontinuation of Investigational Product

Phase 1 studies in patients with end stage renal disease have shown that renal function has a profound effect on plasma concentrations of a major, marginally active metabolite, carboxy-reparixin (DF2243Y), which was found to accumulate over time along with the increased elimination half-life. Even if toxicological results to date suggest that DF2243Y does not raise any safety concern, limited experience in humans recommends discontinuation of the drug in case of renal impairment as it would not be possible to predict the risk associated with elevated plasma levels.

Because reparixin undergoes extensive hepatic metabolism, hepatic dysfunction should also be monitored to avoid an increase in plasma levels. An asymptomatic, self-limited transaminitis is consistently seen after islet transplantation into the liver. This is characterized by elevation in AST/ALT which peaks at about 7 days post transplant and spontaneously normalizes within 4 weeks. Bilirubin and other liver function tests remained within the normal range, suggesting no major hepatic dysfunction that would impact reparixin metabolism. [Rafael, 2003; Barshes, 2005].

Therefore, the Investigational Product should be immediately discontinued in case the patient develops renal or hepatic dysfunction defined as:

**Renal dysfunction:** the occurrence of both CLcr < 60 mL/min **and** urine output < 0.5 mL/kg/hour on two consecutive samplings. Transient alterations of serum creatinine or urine output, other than defined above, do not indicate a renal dysfunction that would cause impaired excretion of DF2243Y.

**Hepatic dysfunction:** the occurrence of ALT/AST > 3 x ULN **and** total bilirubin > 3mg/dL [> 51.3 µmol/L].

Renal and hepatic function will be evaluated daily from post-operative day 1 during Investigational Product infusion. Samples will be processed immediately and results made available as soon as possible to the Investigator.

Additionally, the Investigational Product should be immediately discontinued in the event of any other possibly drug related occurrences that the Investigator believes might compromise patient safety.

Lastly, the Investigational Product will be immediately discontinued in the case the patient withdraw his/her consent or has not received the transplant.

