## 7.5.2 Secondary Variables

### 7.5.2.1 Area Under the Curve for C-peptide During First 4 Hours of a Mixed Meal Tolerance Test

C-peptide is to be collected at 9 time points (2 basal measurements and at 15, 30, 60, 90, 120, 180, and 240 minutes) during the first 4 hours of a mixed meal tolerance test on both Days 75 and 365 after IAT. For both Days 75 and 365, the area under the curve normalized by IEQ/kg infused during IAT will be computed as described in Section 5 of this SAP. AUC values at each day will be summarized descriptively by treatment group.

Analysis will be performed in two steps. First, the AUC normalized by IEQ/kg infused during IAT at each day will be compared between treatment groups using the t-test (two-sided tests at the 5% level of significance).

Second, the AUC normalized by IEQ/kg infused during IAT at the two days will be analyzed by a repeated measurements model using PROC MIXED within SAS®. The model will include fixed effect terms for site, time (Days 75 and 365), and treatment. Time will be specified as a repeated measurement. In order to select an appropriate matrix for the observations within each patient, 3 models will be fitted using the compound symmetry, Huynh-Feldt, and unstructured covariance structures. The matrix for the final model will be selected using Akaike's Information Criterion where the lowest value indicates the best fit. Type III sums of squares from the mixed procedure within SAS® will be used to assess the significance of individual terms within the model using the selected matrix structure. The importance of the treatment-by-site interaction will be investigated and if the term is not significant at the 0.10  $\alpha$ -level, it will be excluded from the model. A logarithmic transformation of the data will be considered if found to be more suitable.

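### The AST/ALT model fixes one variance for Days 1-7 and Day 75, so the Day 75 treatment interval is too wide if, as the protocol's expected course implies, enzymes vary more in the surge week

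*SAP*

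**What the plan says.** SAP 7.6.2.2 states: "Change from baseline (screening) will be analyzed within a single repeated measurements model (for each of AST and ALT) using PROC MIXED". The time factor has eight levels, Days 1 to 7 and Day 75. The model has site, time, treatment and treatment by time, a conditional treatment-by-site term, and "baseline value as a covariate; and a random effect for patient". The covariance is set in advance: "A compound symmetry covariance structure will be used to account for the multiple observations from the same patient". Adjusted differences with 95% intervals are given for each day, and "The treatment effect within each day will be tested using a two-sided test at the 5% level". The section names no alternative structure, selection rule, robust variance or transformation. The contents list of the SAP addendum shows no safety section.

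Protocol 6.3.2 describes the expected course after islet infusion as an "elevation in AST/ALT which peaks at about 7 days post transplant and spontaneously normalizes within 4 weeks". Protocol 8.5 treats ALT/AST up to 5 x ULN within 2 weeks of transplant as routine and exempts it from adverse event recording.

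The SAP is more flexible elsewhere. For the C-peptide AUC model in 7.5.2.1, "3 models will be fitted using the compound symmetry, Huynh-Feldt, and unstructured covariance structures", with the choice made by AIC and a log transformation allowed. The insulin-requirement and time-course models (7.5.2.2, 7.5.2.3) follow the same rule, and the weight model in 7.6.3 leaves the structure open. Among the mixed models in the SAP, only AST/ALT has compound symmetry fixed.

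**The concern.** Compound symmetry assumes the same variance at all eight time points. The protocol describes a first week in which enzymes rise, by routine amounts of up to several times the upper limit. It then describes a return to normal by 4 weeks, which is 47 days before Day 75. Spread in such data usually follows level, so equal variance in the surge week and at Day 75 conflicts with the protocol's own expectation.

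Pooling the variances then carries surge-week noise into the Day 75 interval. Day 75 is the only scheduled AST/ALT measurement after discharge, so a lasting difference between arms could fail to show in the planned test, and a wide interval around zero could be read as reassurance. These are the only planned formal between-arm tests of AST/ALT: at discharge, SAP 7.6.2.1 only counts out-of-range values.

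**Working it through.** The documents state no SD, standard error or power for AST/ALT, so there is no planned figure to reproduce.

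**Inputs.** Eight time points and a two-sided 5% test at each (SAP 7.6.2.2). About 50 patients per arm (100 transplanted, 1:1; SAP 3.1). The SD ratio between surge days and Day 75 is an assumption, shown as a range with Day 75 SD = 1.

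**Formulas.** With complete, balanced data the compound-symmetry variance is the mean of the eight day variances.

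- Model SE, same at every day: sqrt(2 × mean(SD²) / n)
- True SE at day t: sqrt(2 × SD_t² / n)
- R = model SE / true SE = sqrt(mean(SD²)) / SD_t, which does not depend on n
- Actual type I error of the nominal 5% test: 2 × (1 − Φ(1.96 × R))

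**Equal spread on Days 1-7, SD ratio k to Day 75.** Mean variance = (7k² + 1) / 8. For k = 2 this is 29/8 = 3.625, with square root 1.904. R is then 1.904 at Day 75 and 1.904/2 = 0.952 on surge days.

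| k | R at Day 75 | Type I error, Day 75 | R on surge days | Type I error, surge days |
|---|---|---|---|---|
| 1 | 1.00 | 5.0% | 1.00 | 5.0% |
| 1.5 | 1.45 | 0.5% | 0.965 | 5.9% |
| 2 | 1.90 | 0.02% | 0.952 | 6.2% |
| 3 | 2.83 | about 0 | 0.943 | 6.5% |
| 5 | 4.69 | about 0 | 0.938 | 6.6% |

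As k grows, R on surge days tends to sqrt(7/8) = 0.935, so surge-day type I error cannot exceed 6.7% under this profile.

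**Power at Day 75.** A difference with 90% power under the correct SE lies 1.96 + 1.28 = 3.24 true SEs from zero. At 50 per arm that is 3.24 × sqrt(2/50) = 0.65 Day 75 SDs. Under compound symmetry:

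- k = 1.5: Φ(3.24 − 1.96 × 1.447) = Φ(0.40), about 66%
- k = 2: Φ(3.24 − 1.96 × 1.904) = Φ(−0.49), about 31%

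**Spread varying within Days 1-7.**

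- SD rising evenly from 1 on Day 1 to 3 on Day 7: mean variance 4.01, square root 2.003. Day 7 has R = 0.668 and type I error 19%. Day 75 has R = 2.0 and type I error 0.01%.
- Rising to 5 on Day 7: mean variance 9.56, square root 3.091. Day 7 has R = 0.618 and type I error 23%. Day 75 has R = 3.1 and type I error about 0.
- Early peak (SD 5, 4, 3, 2, 2, 2, 2, then 1): mean variance 67/8 = 8.375, square root 2.894. Day 1 has R = 0.579 and type I error 26%. Day 75 has R = 2.9.

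**Checks.** Simulation (50 per arm, within-patient correlation 0.3 and 0.6, 4,000 runs each, site and baseline left out) agreed: in the rising-to-5 case, 22-24% at Day 7 and 0% at Day 75. With a separate variance for each day, type I error was 4.1% to 5.7% at every day in every scenario. One REML random-intercept fit (surge SD 5, Day 75 SD 1) gave SE 0.933 on all eight days, against true SEs of 1.00 and 0.20. With 15% of Day 75 values missing the fitted SEs were 0.942 and 0.993, so the common SE is exact only with complete data, but Day 75 stays about as wide as the surge days.

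**The case against.** The strongest reply is that this is a secondary safety display. Protocol 9.4.3 asks only that AST/ALT be presented, so the test is an SAP addition. It lies outside the testing sequence of SAP 7.3, and neither the discontinuation criteria nor the DMC guidelines use its p-values. SAP 7.6.2.2 also gives descriptive statistics by arm at each day and box plots, so a reader can form a correct Day 75 interval from the reported means and SDs. All of this stands and limits the weight of the point. It does not make the planned intervals correct.

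The size of the error also rests on SDs that the documents do not give, and the protocol describes level, not spread. That stands too, which is why the results are a range. The direction at Day 75 needs only that the Day 75 variance be below the mean of the eight.

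Several stronger readings are not supported:

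- A reader might infer serious over-calling throughout the surge week. With equal spread on Days 1-7 the excess is at most 1.7 percentage points. Large inflation needs further assumed variation within that week, and the 26% figure needs spread to be greatest on Day 1, which fits poorly with a peak at about Day 7.
- A reader might infer that the trial has no other look at lasting liver effects. The Day 75 summaries and box plots remain, and serious adverse events are captured to Day 365.
- A reader might think that unequal correlations (adjacent days against Day 1 with Day 75) drive the error. With complete data the single-day SE contains no correlation term.
- A reader might hold that a log scale is needed. Skewness is plausible, but the documents show no distribution, and unequal variance can be handled without it.

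The random patient effect is redundant, because a random intercept implies the same pattern as compound symmetry. It has not been shown to change any daily estimate or SE.

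**Conclusion.** Wrong as written, with limited reach. Fixed compound symmetry conflicts with the course the protocol expects. The robust consequence is a Day 75 interval that is too wide: 1.45 to 4.7 times at assumed SD ratios of 1.5 to 5 with a flat surge week. Over the same range surge-day error stays close to nominal. Peak-day type I error of roughly 19-26% arises only if spread also varies within Days 1-7, at assumed ratios of 3 to 5. If the SDs were in fact equal at all eight days there would be no error. The main efficacy conclusions are untouched; what is affected is the planned formal comparison of AST and ALT between arms.

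**What to change.** In SAP 7.6.2.2, replace fixed compound symmetry by an unstructured covariance, and name heterogeneous compound symmetry as the fallback if the model does not converge. An acceptable alternative is the AIC rule of 7.5.2.1, limited to structures that let the variance differ by day (Huynh-Feldt and unstructured). Remove the random patient effect from this model. A log-scale analysis may be added as an option, as 7.5.2.1 already allows for efficacy, but is not required.

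The cost is a short change to the SAP text and a few lines of code, with no new data. The downside is more covariance parameters: 8 × 9 / 2 = 36 for unstructured, feasible with about 100 patients measured up to eight times, and 8 + 1 = 9 for the fallback.

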#### 7.6.2.3 Albumin and Pre-albumin

Serum levels of albumin and pre-albumin are collected pre-transplant and on Day 75 ± 14 days and Day 365 ± 14 days. Each parameter will be summarized descriptively at each time point and change from pre-transplant to post-transplant time points (post-transplant value minus pre-transplant value) will be summarized descriptively by treatment group and in total.

Observed values will also be presented as box plots for each treatment group at each time point

### 7.6.3 Vital Signs

Vital signs, including systolic and diastolic blood pressure and heart rate, are measured at pre-transplant hospital admission (screening) and post-transplant hospital discharge. Each of these three parameters will be summarized descriptively at each time point and change from hospital admission to hospital discharge will be summarized descriptively by treatment group and in total.

Weight is collected at screening, Day 75, and Day 365. Observed values at each visit and change from screening to each follow-up visit will be summarized descriptively by treatment group and in total. Change from baseline (screening) will be analyzed as repeated measures with a single repeated measurements model using PROC MIXED within SAS®. The model will include fixed effect terms for site, time (Days 75 and 365), and treatment; the treatment by time interaction; the treatment by study site interaction if significant at the 0.10  $\alpha$ -level; baseline weight

REP0112

Statistical Analysis Plan

as a covariate; and a random effect for patient. An appropriate covariance structure will be selected.

The adjusted least squares means and associated 95% confidence intervals will be estimated for each combination of day and treatment, and the adjusted least squares mean difference (reparixin minus placebo) and associated 95% confidence interval at each day will also be estimated. The treatment effect within each day will be tested using a two-sided test at the 5% level. The tests of the fixed effects in the model will also be presented.

#### **7.6.4 Steatorrhea Severity**

Summarization and analysis of steatorrhea severity will be performed separately at Day 75 and Day 365 after IAT by treatment group and in total. The number and percentage of patients in each steatorrhea severity category and the associated 95% confidence interval for the proportion of patients in each category will be presented.

#### **7.6.5 Malnutrition Risk Level**

Summarization and analysis of malnutrition risk level will be performed separately at Day 75 and Day 365 after IAT by treatment group and in total. The number and percentage of patients in each malnutrition risk level and the associated 95% confidence interval for the proportion of patients in each level will be presented.

#### **7.6.6 Documented Hypoglycemic Episodes**

The cumulative number of documented symptomatic hypoglycemic episodes and the cumulative number of asymptomatic hypoglycemia episodes occurring from Days 75 to 365 inclusive after IAT will be summarized descriptively by treatment group and in total. The cumulative number of episodes for a patient will be the number of episodes recorded on CRF Page 27.1. Treatment groups will be compared using a two-sided t-test or non-parametric Wilcoxon rank-sum test.

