Based on these considerations, it is planned to enroll 100 patients in this trial who receive IAT, with the expectation that there will be approximately 5 others who do not receive IAT. Under such a plan, the trial would not be overpowered even if all participants were in the 2500-5000 IEQ/kg stratum since statistical significance (i.e., one-sided  $p=0.025$ ) would be obtained with 52 patients per arm if the estimated difference is 23.1% (12/52) versus 42.3% (22/52), which is an estimated clinically significant 19.2% increase in percentage of patients achieving insulin independence.

The sample size of 100 to 105 patients also provides high statistical power for the key secondary endpoint, C-peptide area under the curve (AUC) (mixed meal tolerance test [MMTT]) normalized by IEQ/kg. Based on preliminary data reported from the ongoing pilot trial, Month 1 post transplant means and standard deviations for this endpoint are  $1.92 \pm 1.62$  in the reparixin group and  $0.44 \pm 0.04$  in the control group. With 52 patients in each treatment group, the trial will have greater than 95% power to detect a difference in means of at least 1.48 (the difference between a treated mean of 1.92 and a control mean of 0.44) assuming that the common standard deviation is 1.37 and using an 0.0025 two-sided significance level.

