### 3.4 Randomization

Patients will be randomized in a 1:1 fashion to either reparixin or placebo.

The randomization list will be generated with a computer procedure by the method of random permuted blocks in which treatment (in blocks of 4) will be balanced within centres. A master randomization list will be generated, randomizing an excess of patients (a maximum of 40 for each site) to allow competitive recruitment within each centre.

The randomization list will be prepared by an independent statistician and provided to Dompé in a sealed envelope to prevent unblinding.

Similarly, individual treatment codes will be provided via a tamper-resistant system (either a sealed envelope or a scratch card). Such a system will definitely allow recognition of whether the code has been broken and guarantees detection of any code misuse. Individual treatment codes will be provided to:

- the Pharmacist (or designee) within each participating site for investigational product preparation;
- the Dompé Pharmacovigilance Department for safety procedures.

The investigators can request to an independent facility (either by telephone or web based system) an individual code in the event of an emergency only, where knowledge of the blinded treatment for that patient could influence further patient care. Any potential unauthorized code break and the reason behind it will be recorded.

The randomization codes will also be accessible to an independent statistician (liaison between the contract research organization [CRO] database and Data Monitoring Committee [DMC] biostatistician) who will generate the reports for the DMC evaluation.

The randomization code will be broken at study completion, i.e. when the last patient has completed his/her last follow-up visit (planned at 365 days after islet infusion), and once the database has been locked.

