## 5 DEFINITIONS AND DERIVED VARIABLES

Study Day Relative to Date of First Date of Investigational Product Administration: Day 1 will be defined as the first date on which infusion of investigational product is started. Positive study days will be counted forward from Day 1. Day -1 will be the date immediately preceding Day 1, and negative study days will be counted backward from Day -1.

Study Day Relative to Date of Islet Auto-Transplantation: Day 0 will be defined as the date on which islet are infused. Positive study days will be counted forward from Day 0. Day -1 will be the date immediately preceding Day 0, and negative study days will be counted backward from Day -1.

Visit Windows: For the per protocol population (see Section 6 of this SAP), data recorded at the Day 75 and Day 365 visits will be included in summarization and analysis only if the Day 75 and Day 365 visits fall within 14 days of the target study day relative to the date of IAT as indicated in the following table.

Visit	Target Study Day Relative to Date of IAT	Acceptable Range of Study Days Relative to IAT
Day 75	75	61 to 89
Day 365	365	351 to 379

Area Under the Curve (AUC) Normalized by the Number of IEQ/kg, C-peptide: When C-peptide values are below the limit of detection (0.05 ng/mL), a value of 0.05 ng/mL will be assumed in the calculation of area under the curve. Missing C-peptide values will be imputed via linear interpolation, and the average of the two basal samples (values, and mid-point of sample times) will be used as the first sample in the computation of the AUC. Once these rules have been applied to the data, AUC for C-peptide will be computed using the trapezoidal rule, and normalized by dividing the computed AUC value by the total IEQ/kg infused during IAT as recorded on Page 12 of the CRF. For ease of interpretation, the AUC value obtained will be divided by the total time the scale is assessed for reporting purposes. Computation of AUC will be based on actual collection times, unless actual collection time is missing, in which case the scheduled collection time will be used.

REP0112

Statistical Analysis Plan

Other definitions and derived variables are found within the applicable subsections of Section 7, Statistical Methods.

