## 7 STATISTICAL METHODS

### 7.1 General Principles

The statistical package SAS® will be used to produce all summary tables, figures, and listings.

In general, categorical data will be presented using counts and percentages, whilst continuous variables will be presented using the number of patients, mean, standard deviation, median, minimum, and maximum. Denominators for calculation of percentages will be taken as the number of non-missing responses in the specified analysis population and treatment group unless otherwise stated, and percentages will be rounded to one decimal. Minima and maxima will usually be reported to the same level of accuracy as the raw data; means, medians and standard deviations will be presented to one further decimal place; standard errors (if presented) will be presented to 2 decimal places more than the raw data.

REP0112

Statistical Analysis Plan

All data recorded in the CRF will be listed.

Unless otherwise specified, the significance level used for statistical testing will be 5% and two-sided tests will be used.

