#### 7.5.2.6 Cumulative Number of Severe Hypoglycemic Events From Day 75 to Day 365 After IAT

The cumulative number of severe hypoglycemic events from the Day 75 to Day 365 visits (as recorded on CRF Page 24.1) will be summarized descriptively by treatment group.

The effect of treatment on the rate of recurrent episodes of severe hypoglycaemia will be evaluated using an Andersen-Gill analysis with robust sandwich-type variance estimate. From the model, the estimated hazard ratio (reparixin versus placebo), associated 95% confidence interval, and a two-sided p-value assessing the significance of the hazard ratio (at the 5% level) will be presented.

#### 7.5.2.7 Proportion of Patients With HbA1c $\leq$ 6.5% at Day 365 and Free of Severe Hypoglycemic Events From Day 75 Through Day 365

HbA1c for Day 365  $\pm$  14 days after IAT and the number of severe hypoglycemic events from Day 75 through Day 365 will be recorded on CRF Page 24.1, and these values will be used for summarization and analysis. The number and percentage of patients with HbA1c  $\leq$ 6.5% at Day 365  $\pm$  14 days after IAT and who are free of severe hypoglycemic events from Day 75  $\pm$  14 days to Day 365  $\pm$  14 days after IAT, the 95% confidence interval for the proportion, the treatment effect (reparixin percentage minus placebo percentage), and the 95% confidence interval for the treatment effect will be presented by treatment group. The percentage of patients with HbA1c  $\leq$ 6.5% at Day 365  $\pm$  14 days after IAT and who are free of severe hypoglycemic events from Day 75  $\pm$  14 days to Day 365  $\pm$  14 days after IAT will be compared between treatment groups using the Pearson chi-squared test (two-sided testing at the 0.05 level of significance). If assumptions regarding expected cell counts are not met, Yate's correction will be applied.

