#### **7.6.7 Diabetic Ketoacidosis-related Events**

The cumulative number of diabetic ketoacidosis-related events occurring from Days 75 to 365 inclusive after IAT will be summarized descriptively by treatment group and in total. The cumulative number of diabetic ketoacidosis-related events for a patient will be the number of events recorded on CRF Page 27.1. Treatment groups will be compared using a two-sided t-test or non-parametric Wilcoxon rank-sum test.

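### Documented hypoglycaemia and ketoacidosis are compared as raw counts, with follow-up time unused and the choice between t-test and Wilcoxon left open

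*SAP*

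**What the plan says.** SAP 7.6.6 defines the hypoglycaemia variable, separately for symptomatic and asymptomatic episodes: "The cumulative number of episodes for a patient will be the number of episodes recorded on CRF Page 27.1". SAP 7.6.7 does the same for ketoacidosis: "The cumulative number of diabetic ketoacidosis-related events for a patient will be the number of events recorded on CRF Page 27.1". Both sections then give the same instruction: "Treatment groups will be compared using a two-sided t-test or non-parametric Wilcoxon rank-sum test". Neither mentions time at risk, a rate, early withdrawal or a criterion for picking the test. SAP 7.2 leaves missing-data handling to the individual analysis sections, and these two contain none.

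SAP 7.6 assigns these analyses to the safety population, which SAP 6 defines as all randomized patients. SAP 5 restricts data by visit window in one population only: "For the per protocol population (see Section 6 of this SAP), data recorded at the Day 75 and Day 365 visits will be included", subject to the window. Protocol 4.2.3 runs both counts from the Day 75 visit to the Day 365 visit, each ±14 days. Protocol 7.2 collects documented hypoglycaemia from glucometer downloads or glucose logs covering the time between visits.

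For severe hypoglycaemia over the same interval, SAP 7.5.2.6 has the event rate "evaluated using an Andersen-Gill analysis with robust sandwich-type variance estimate". Protocol 9.4.3 plans only descriptive statistics for documented hypoglycaemia and ketoacidosis. The comparative tests first appear in the SAP, although SAP 1.2 records no change from the protocol. The SAP Addendum's table of contents has no safety section.

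**The concern.** A count depends on how long the patient was observed as well as on the event rate. Both planned tests compare counts as if everyone had been observed equally long. Should one arm be observed for less time, and should its early leavers enter with whatever they had accrued, that arm's counts fall for a reason unrelated to the drug. In a safety comparison this makes the arm that loses more patients look better.

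The second gap needs no imbalance. With two tests allowed and no rule between them, the choice can be made after both p-values are known.

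**Working it through.** The documents give no event rate, power or dropout figure for these analyses, so there is no stated figure to reproduce. The check has four steps.

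**1. How much observation time varies among completers.** SAP 5 allows Days 61 to 89 for the first visit and Days 351 to 379 for the second.
- Shortest interval: 351 − 89 = 262 days.
- Target: 365 − 75 = 290 days.
- Longest: 379 − 61 = 318 days.
- Ratio of longest to shortest: 318 / 262 = 1.21.

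**2. How dropout shifts a mean count.** Assume dropout times are uniform over the interval and that leavers keep their partial count. An arm with dropout proportion d is then observed for an average fraction 1 − d/2 of the interval. With no drug effect the expected count ratio is (1 − d₁/2) / (1 − d₂/2):
- 20% vs 10%: 0.90 / 0.95 = 0.947
- 30% vs 10%: 0.85 / 0.95 = 0.895
- 40% vs 10%: 0.80 / 0.95 = 0.842

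**3. What that does to the tests.** Inputs from the SAP:
- Allocation (3.4): "Patients will be randomized in a 1:1 fashion to either reparixin or placebo".
- Size (3.3): "it is planned to enroll 100 patients in this trial who receive IAT, with the expectation that there will be approximately 5 others", meaning patients without a transplant. The simulation used 50 per arm.
- Level (7.1): "the significance level used for statistical testing will be 5% and two-sided tests will be used".

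Assumed inputs:
- gamma-Poisson counts with variance = mean + dispersion × mean², dispersion 0.5 or 1;
- means of 5, 20 or 50 events per 290 days, and 0.1 to represent a rare event such as ketoacidosis;
- dropout of 0% to 40% per arm.

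There were 2,000 replicates per scenario, so the Monte Carlo standard error at 5% is √(0.05 × 0.95 / 2000) ≈ 0.5 points. False-positive rates for means of 5 to 50:

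| Dropout by arm | Count ratio | t-test | Wilcoxon |
|---|---|---|---|
| Equal, 0% to 20% | about 1.00 | 4.5–5.4% | 4.5–5.6% |
| 20% vs 10% | about 0.95 | 5–7% | 5–7% |
| 30% vs 10% | about 0.90 | 7–10% | 9–13% |
| 40% vs 10% | about 0.84 | 12–19% | 15–25% |

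A log rate-ratio test on events per patient-day with robust variance gave 4.6–6.8% across all these dropout scenarios. It stands in for any method that uses the time denominator; it is not the negative binomial model itself.

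Visit windows alone matter only if they line up with treatment. Placing all of one arm at 318 days and all of the other at 262 (mean 20, dispersion 0.5) gave a count ratio of 1.21, with 24% (t-test) and 21% (Wilcoxon) false positives. This is an outer bound, not an expectation.

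At the assumed mean of 0.1 the count ratio shifts just as much, but false positives stay at 4–6%. The robust rate test is itself conservative there, at about 1–2%, which is why a large-sample rate test does not suit ketoacidosis.

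**4. The open choice of test.** With equal follow-up and means of 5 to 50, declaring significance on the smaller of the two p-values gave 6.2–7.8% instead of 5%.

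**The case against.** The strongest reply is that nothing in the documents predicts unequal follow-up between arms. The trial is double-blind and randomized 1:1 in blocks within centre, so follow-up is equal in expectation and each test, taken alone, holds its level. Protocol 9.4.6 expects very few patients to be lost. The retention worry in SAP 7.5.1 is about differences between sites, not arms. Protocol Appendix 5 applies the ±14-day window to every patient's visits; only the analysis exclusion is confined to the per protocol set. All of this stands.

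The mechanism is also unproven. The count is whatever is recorded on CRF Page 27.1. SAP 7.5.2.2 uses Page 24 for Day 75 and Page 24.1 for Day 365, so by analogy Page 27.1 may be completed only at the Day 365 visit. The CRF is not available to settle this. A patient who leaves early might then have no count at all. The problem would become selection of completers, which an offset does not repair and which the plan does not address either. A reader might infer that the arm with more early leavers will look safer; the documents do not establish that.

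Two further points stand. An offset in days does not adjust for how often patients test their glucose, which affects asymptomatic episodes. Severe hypoglycaemia is an efficacy endpoint in the SAP 7.3 sequence, so a fuller model there is not in itself a contradiction.

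None of this supplies a rule for choosing the test or for handling early leavers. SAP 7.2 and 7.4.1 would show missing data and withdrawals by arm, so a large imbalance would be visible, but the comparison would remain unadjusted.

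**Conclusion.** The gap is real and minor. Both sections leave follow-up time unused and the test unspecified. The effect on the comparison is conditional: it needs follow-up to differ between arms and early leavers to keep partial counts. Under the assumed event rates the inflation is small for a 10-point dropout gap (5–7%), clear at 20 points (7–13%) and absent with equal dropout. The open choice of test costs about 6–8% against a nominal 5% without any imbalance, if the smaller p-value is the one reported.

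Two stronger readings should be resisted. One is that the planned comparison is biased as it stands: randomization and blinding argue against that, and the documents give no dropout by arm. The other is that ketoacidosis p-values are unreliable for this reason: at an assumed mean of 0.1 they barely move, and only the estimate is affected.

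Event means, dispersion, dropout rates and dropout timing are all assumptions. The endpoints lie outside the SAP 7.3 testing sequence, so the primary conclusion is unaffected.

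**What to change.** Amend SAP 7.6.6 and 7.6.7 before database lock.

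- **Documented symptomatic and asymptomatic episodes:** name one method. Either use negative binomial regression with log(days over which episodes were ascertained, from the Day 75 visit to the Day 365 visit or last ascertainment) as offset, or Andersen-Gill as in SAP 7.5.2.6. Report the rate ratio with its 95% confidence interval.
- **Ketoacidosis:** report events per patient-year by arm with an exact rate comparison. The gain is in the estimate, not the p-value.
- **Missing counts:** state that a patient with no count on Page 27.1 is missing, is reported as such by arm, and is not counted as zero.
- **No transplant:** state that patients who never receive IAT have no time at risk for this interval.
- **Change record:** list the comparison in SAP 1.2 as an addition to Protocol 9.4.3.

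The cost is SAP wording and some programming, plus a model assumption that the rank test does not make. Visit dates are already recorded under Protocol 7.2. For early leavers, the date up to which episodes were ascertained must be confirmed as available; if it is not, those patients fall under the missing-count rule.
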